- TEV-48574 [REDACTED]
- Placebo to match TEV-48574

With randomization, patients enter the 16-week treatment period. The patients will receive the IMP loading dose on the day of randomization and the subsequent corresponding IMP maintenance dose every 2 weeks for a total of 8 doses (1 loading dose and 7 maintenance doses).

Patients qualifying for randomization will continue the same background asthma controller regimen as used during run-in without change for the first 4 weeks of the treatment period; this regimen includes study-provided controller inhalers (ICS+LABA and additional ICS), plus any additional controller medications that met the eligibility criteria. After week 4, background asthma controller therapies will be decreased in a structured manner in patients not experiencing LoAC (see Section 6.1.1 for LoAC definition) (the patient will be aware of the dose decreases). The first step is implemented after the first 4 weeks of the treatment period and includes discontinuing LABA and any additional asthma controller medications, with the exception of study-provided additional ICS. The second step will be made 2 weeks later. The second and subsequent steps will consist of decreasing the ICS dose step-wise weekly, by ~50%. For patients on ICS doses greater than the high dose ICS+LABA twice a day, the total ICS dose should also be decreased step-wise weekly, by ~50%. Excluding patients who meet LoAC criteria during the structured withdrawal of background asthma controller therapies, the duration of treatment with IMP only will be approximately 8 or 9 weeks. Since study-provided asthma controller formulations may vary locally, Table 1 shows an example of the step-wise structured withdrawal. Eligibility assessment for structured withdrawal of background asthma controller therapies (between scheduled in-person visits) may be done by phone; if it is suspected that a patient meets the criteria for LoAC, the investigator may ask the patient to attend the site for an unscheduled visit.

Table 1: Examples of Schedule of Withdrawal of Background Asthma Controller Therapies

Time point: Weeks after randomization (visit number)	Action	Dose at start of treatment period	
		Fluticasone/salmeterol 500/50 µg BID	Fluticasone/salmeterol 250/50 µg BID
4 weeks (V3)	Discontinue LABA and other non-ICS asthma controllers*	FP 500 BID	FP 250 BID
6 weeks (V4)	First ICS decrease	500 decreased to 250 BID	250 decreased to 100 BID

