7 weeks (Telephone, V5)	Second ICS decrease	250 decreased to 100 BID	100 BID decreased to 0
8 weeks (V6)	Third ICS decrease	100 BID decreased to 0	0

*Other asthma controllers (eg, LAMA, leukotriene antagonists) will also be discontinued.

Note: Last IMP administration 14 weeks after randomization (visit 9); end-of-treatment visit (EOT) 16 weeks after randomization

BID=twice daily; FP=fluticasone propionate; ICS=inhaled corticosteroids; LABA=long-acting beta-agonists; LAMA= long-acting muscarinic antagonist; V = visit.

Patients will be monitored for worsening of asthma and potential LoAC (and CAE) both at scheduled visits and in between visits via hand-held spirometry and e-diary. Asthma specific alerts will be sent for the following:

- Decrease in morning FEV₁ $\geq 20\%$ from baseline on 2 consecutive days OR decrease in morning PEF $\geq 30\%$ from baseline on 2 consecutive days
- Increase in rescue medication use/SABA of 4 or more puffs over baseline for 2 or more consecutive days OR ≥ 12 puffs in any single day
- Increase of 2 nighttime awakenings due to asthma over baseline on 2 consecutive days

In the event of an alert, the site will follow-up with the patient. An alert does not mean that the patient's medications need to be changed or that study drug should be discontinued, only that the patient should be contacted and evaluated by phone or at an unscheduled visit according to investigator judgment. If, in the investigator's judgment, LoAC is suspected, every effort to have the patient evaluated at an unscheduled visit should be made.

Definitions of LoAC and Clinical Asthma Exacerbation (CAE) are presented in Section 6.1.1 and Section 6.1.2. LoAC events and CAEs will be treated by the investigator according to local standard of care. In the event of a LoAC or CAE, IMP will be discontinued and background asthma controller therapy will be restarted or increased per investigator judgment. Patients who experience LoAC or CAE will remain in the study for assessments. (Note: CAEs are a subset of LoAC events; see Section 6.1.1 and Section 6.1.2 for definitions).

Study procedures and assessments are described in detail Section 3.6.

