- ^b In case of early termination the procedures outlined in Section 3.6.1.2.9 should be followed.
- ^c If, in the investigator's judgment, LoAC is suspected, every effort to have the patient evaluated at an unscheduled visit should be made. Procedures and assessments to be performed if an unscheduled visit occurs are described in Section 3.6.1.4. An effort should be made to collect blood samples for TEV-48574 serum concentration and ADA testing at (or as close to) the time of LoAC as possible in addition to the scheduled assessments.
- ^d At the visits it should be determined if the patient has adequate rescue medication remaining.
- ^e If a patient exhibits clinical symptoms during the study that may indicate COVID-19 infection, the patient will be tested for active COVID-19 infection. If the patient tests positive, the patient will be discontinued from IMP and will need to visit the clinical site again for an early termination visit. Remote assessment of safety via teleconference and/or videoconference, with videoconference being the preferred method, is recommended until the patient is able to visit the clinical site for the early termination visit.
- ^f ECG assessments should precede vital sign assessments. ECGs should be performed in a supine position after 5 minutes rest. At DoR, ECG will be performed in triplicate, with each ECG taken within 1 to 5 minutes of the previous one.
- ^g Vital signs measurements include blood pressure, pulse, body temperature, and respiratory rate. Patients are to remain in a supine position for at least 5 minutes prior to measuring blood pressure and pulse. If possible, blood pressure measurements should be completed on the same arm at each visit. Vital signs should be measured before scheduled blood draws and after the ECG assessment when applicable.
- ^h For details on full/brief physical examinations, see Section 7.7.
- ⁱ FeNO should be completed before in-office spirometry.
- ^j A structured decrease in background asthma controller therapies will be performed as described in Section 3.1 in patients without LoAC. Further details can be found in the pharmacy manual.
- ^k Only for women of childbearing potential.
- ^l When sampling urine, menstruation status should be recorded for women of childbearing potential.

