3.6.1.2.3. Treatment Visit 3 (Week 4)

At this study visit, patients who have not had LoAC will begin the structured withdrawal of their background asthma controller therapies.

Efforts should be made to perform the following assessments and procedures in the order listed:

- Perform concomitant medication inquiry.
- Perform adverse event inquiry.
- Perform COVID-19 symptoms inquiry.

- Review daily e-diary for SABA/quick-relief medication usage and nighttime awakenings, including for adherence.
- Review daily hand-held spirometry, including for adherence.
- Perform LoAC and CAE inquiry.
- Patients who have not had LoAC will commence the structured withdrawal of their background asthma controller therapies (see Section 3.1).
- Complete the ACQ-6.
- Check supply and, if required, dispense study-provided controller therapies. Collect returned inhalers.
- Check supply of study-provided SABA. Collect returned inhalers.
- Perform ECG.
- Perform vital signs measurements (includes systolic and diastolic blood pressure, pulse, body temperature, and respiratory rate).
- Perform brief physical examination.
- Measure FeNO.
- Perform in-office spirometry (full flow-volume loop).
- Perform urine pregnancy testing (women of childbearing potential).
- Collect samples for clinical laboratory tests (serum chemistry, CBC with differential count, peripheral eosinophil count).
- Collect blood for serum TEV-48574 concentration determination (PK assessment) from all patients.
- Collect blood sample for immunogenicity (ADA) assessment.
- Collect blood sample for [REDACTED] assessment.

The following procedures/assessments will be performed during and after administration of study drug:

- Administer IMP [REDACTED] using the [REDACTED]
- [REDACTED]
- Evaluation of local tolerability at 1-hour post-administration.
- If, during administration or during post-IMP administration observation the patient develops clinical symptoms or signs, vital signs should be collected and a physical exam (brief or full, at the discretion of the investigator) performed. The patient should be assessed for anaphylaxis/hypersensitivity reactions as detailed in Section 7.1.6.

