3.6.1.2.8. Treatment Visits 7 (Week 10), 8 (Week 12) and 9 (Week 14)

At these study visits, most patients who have not had LoAC will have fully withdrawn their background asthma controller therapies and will continue on IMP only.

Patients who have not had LoAC and are not yet on IMP only (due to the initial ICS dose) will continue the structured withdrawal of their background asthma controller therapies.

Efforts should be made to perform the following assessments and procedures in the order listed at each of these visits, unless otherwise indicated:

- Perform concomitant medication inquiry.
- Perform adverse event inquiry.
- Perform COVID-19 symptoms inquiry.
- Confirm that all background asthma controller therapies have been discontinued, as scheduled.
- Review daily e-diary for SABA/quick-relief medication usage and nighttime awakenings, including for adherence.
- Review daily hand-held spirometry, including for adherence.
- Perform LoAC and CAE inquiry.
- Patients who have not had LoAC will continue either on IMP only (Section 3.1) or with structured withdrawal of their background asthma controller therapies.
- Complete the ACQ-6.
- Check supply and, if required, dispense study-provided controller therapies. Collect returned inhalers.
- Check supply of study-provided SABA. Collect returned inhalers.
- Perform ECG (visit 8 only).

- Perform vital signs measurements (includes systolic and diastolic blood pressure, pulse, body temperature, and respiratory rate).
- Perform brief physical examination.
- Measure FeNO.
- Perform in-office spirometry (full flow-volume loop).
- Perform urine pregnancy testing (women of childbearing potential).
- Collect samples for clinical laboratory tests (serum chemistry, CBC with differential count, peripheral eosinophil count; visit 8 only).
- Collect blood for serum TEV-48574 concentration determination (PK assessment) from all patients (visit 8 only).
- Collect blood sample for immunogenicity (ADA) assessment (visit 8 only).

The following procedures/assessments will be performed during and after administration of study drug:

- Administer IMP [REDACTED] using the KORU [REDACTED]
- [REDACTED]
- Evaluation of local tolerability at the administration site at 1-hour post-administration.

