3.6.1.2.9. Early Termination (ET) Visit

Patients who discontinue treatment with IMP for reasons other than the occurrence of LoAC/CAE in the study are encouraged to complete early termination (ET visit) procedures as soon as possible after receiving their last dose of IMP and to complete the remaining study visits and assessments (with the exception of administration of IMP) including EOT and EOS within the original time frames based on day of randomization (DoR). These patients are not considered to have withdrawn from the study.

Patients who decide to withdraw completely from the study are encouraged to complete early termination (ET visit) procedures as soon as possible after receiving their last dose of IMP.

At the ET visit the following procedures/assessments will be performed:

- Perform concomitant medication inquiry.
- Perform adverse event inquiry.
- Perform COVID-19 symptoms inquiry.
- Review daily e-diary for SABA/quick-relief medication usage and nighttime awakenings, including for adherence.

- Review daily hand-held spirometry, including for adherence.
- Perform LoAC and CAE inquiry.
- Complete the ACQ-6.
- Check supply and, if required, dispense study-provided controller therapies (for patients who remaining in the study). Collect returned inhalers.
- Check supply of study-provided SABA (for patients who are remaining in the study). Collect returned inhalers.
- Perform ECG.
- Perform vital signs measurements (includes systolic and diastolic blood pressure, pulse, body temperature, and respiratory rate).
- Perform full physical examination.
- Measure FeNO.
- Perform in-office spirometry (full flow-volume loop).
- Perform urine pregnancy testing (women of childbearing potential).
- Collect samples for clinical laboratory tests (serum chemistry, CBC with differential count, peripheral eosinophil count, urinalysis).
- Collect blood for serum TEV-48574 concentration determination (PK assessment) from all patients.
- Collect blood sample for immunogenicity (ADA) assessment.
- Collect blood sample for ██████████ assessment.

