If a patient exhibits clinical symptoms during the study that may indicate COVID-19 infection, the patient will be tested for active COVID-19 infection. If the patient tests positive, the patient will be discontinued from IMP and will attend for an ET visit. Remote assessment of safety via teleconference (TC) and/or videoconference (VC), with VC being the preferred method, is recommended until the patient attends for the ET visit.

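### The controller taper depends only on absence of LoAC, not on continuing IMP, so patients who stop IMP for another reason could lose their controllers for weeks that the main efficacy analyses do not use

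*Protocol*

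**What the plan says.** Protocol Section 3.1 sets the taper rule: "After week 4, background asthma controller therapies will be decreased in a structured manner in patients not experiencing LoAC". Table 3, footnote j, repeats it: "A structured decrease in background asthma controller therapies will be performed as described in Section 3.1 in patients without LoAC". Visit 3 (Section 3.6.1.2.3) applies it: "Patients who have not had LoAC will commence the structured withdrawal of their background asthma controller therapies". Visits 4 to 9 and the phone contacts use the same single condition. Visits 7 to 9 add a check: "Confirm that all background asthma controller therapies have been discontinued, as scheduled".

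For LoAC or a clinical asthma exacerbation (CAE), Section 3.1 stops IMP and says that "background asthma controller therapy will be restarted or increased per investigator judgment". Section 6.1.1 keeps the regimen fixed until the taper or treatment of LoAC/CAE; stopping IMP is not a listed reason to change it. Otherwise, controllers may be restarted after EOT (week 16).

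IMP can stop without LoAC. Some stops are mandated, for example in Section 4.4.1 for COVID-19: "If the patient tests positive, the patient will be discontinued from IMP and will attend for an ET visit". Appendix J requires another when an outbreak prevents attendance. Patients who stop this way are encouraged to have an ET visit and then to "complete the remaining study visits and assessments (with the exception of administration of IMP) including EOT and EOS". On controllers, the ET list says only to check supply and, if required, "dispense study-provided controller therapies (for patients who remaining in the study". Neither it nor Section 4.4.2 says whether the taper stops or controllers resume.

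**The concern.** Withdrawing controllers is justified because it tests whether IMP can replace them. Once IMP has stopped for good, that reason largely lapses. Yet the remaining visits carry the taper steps, and the only stated test at each step is whether LoAC has occurred. A site following the wording could withdraw ICS and LABA from a patient with severe uncontrolled asthma who is no longer dosed, possibly just after COVID-19.

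What is at stake is patient safety for little scientific return. Under SAP 1.7 and 6.2.2, a patient who stops for an unrelated reason is scored as having no LoAC unless it occurred by last dose plus 14 days. Time to LoAC is censored at withdrawal (SAP 6.3.1). The EOT analysis of ACQ-6 uses the ET visit, and the MMRM analyses discard later observations (SAP 6.3.2).

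**Working it through.** **Inputs.** Taper steps from Protocol Table 1 and visit days from Table 3:
- Start dose 500 BID: days 29 (LABA and other non-ICS controllers stop), 43, 50 and 57; ICS reaches zero at week 8.
- Start dose 250 BID: days 29, 43 and 50; ICS reaches zero at week 7.
- Last dose at week w is day 7w + 1. The SAP 1.7 window closes 14 days later, on day 7w + 15.

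**The plan's own figure.** Section 3.1 gives about 8 or 9 weeks on IMP alone. Table 1 reproduces it: 16 − 8 = 8 and 16 − 7 = 9.

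**Steps still due after the last dose** are those at later visits. **Controller-free weeks after the window closes**, if nothing is restarted before EOT, are 16 − max(w + 2, 8) for 500 BID and 16 − max(w + 2, 7) for 250 BID. Cells show 500 BID / 250 BID.

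| Last dose (week) | Window closes (day) | Steps due | Before closing day | On closing day | After | Controller-free weeks after close |
|---|---|---|---|---|---|---|
| 0 | 15 | 4 / 3 | 0 / 0 | 0 / 0 | 4 / 3 | 8 / 9 |
| 2 | 29 | 4 / 3 | 0 / 0 | 1 / 1 | 3 / 2 | 8 / 9 |
| 4 | 43 | 3 / 2 | 0 / 0 | 1 / 1 | 2 / 1 | 8 / 9 |
| 6 | 57 | 2 / 1 | 1 / 1 | 1 / 0 | 0 / 0 | 8 / 8 |
| 8 | 71 | 0 / 0 | – | – | – | 6 / 6 |
| 10 | 85 | 0 / 0 | – | – | – | 4 / 4 |
| 12 | 99 | 0 / 0 | – | – | – | 2 / 2 |
| 14 | 113 | 0 / 0 | – | – | – | 0 / 0 |

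For a last dose at week 0, 2 or 4, every remaining step falls on or after the closing day, and most fall after it. From week 8 on, the only gap is the missing restart rule. Visits have a ±3-day window, so a step on the closing day could fall either side. Patients entering above high-dose ICS taper for longer and may have steps left after week 8. Table 3 and Section 3.6.1.2.1 place withdrawal of the other controllers at randomization, in conflict with Section 3.1; this does not change the ICS/LABA steps counted.

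**Residual drug.** Section 7.3 equates 5 half-lives with about 10 weeks, so one half-life is about 10/5 = 2 weeks. Assuming exponential decline, a week-2 level falls to 0.5^(5/2) = 18% by week 7 and 0.5^(6/2) = 12.5% by week 8.

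**Resumption against the 4x ICS criterion.** If the taper stops when IMP stops, resuming before Visit 5 (week 7) is at most 500/250 = 2x or 250/100 = 2.5x. After Visit 5 it is 500/100 = 5x, or from zero, where the ratio is undefined. Only these later stops raise a scoring question.

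**Number affected.** The documents give no rate. The 15% allowance is for dropout from the study, and these patients stay in. If, purely as an assumption, their number were 25% to 100% of that allowance, it would be 124 × 0.15 × 0.25 = 4.65 to 124 × 0.15 = 18.6, or about 5 to 19 of 124.

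**The case against.** The taper appears to be written for patients on IMP. Its end state is IMP alone, and a patient off IMP fits neither group described at Visits 7 to 9. Completing visits and assessments does not plainly include withdrawing a medicine. The ET list has no taper step and allows controllers to be dispensed. SAP 1.7 expects patients who stop early to be put on alternative medications. Appendix J lists what continues after an outbreak-related stop and does not name the taper. Footnote j refers to a pharmacy manual that was not available.

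This stands as evidence of intent, and it rules out one tempting reading: that the protocol orders the taper for patients off IMP. It does not. But none of these texts makes continuing IMP a condition or says what happens to controllers when IMP stops. The general discretion in Section 7.1.7 and Appendix J does not mention controllers.

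A reader might also infer that these patients are unprotected. They are not: daily spirometry and e-diary, rescue medication and site follow-up of alerts continue, and some alerts trigger below the LoAC thresholds (4 puffs over baseline against 6). Controllers must be restarted or increased at LoAC. However, that mandatory step comes only after control is lost, and an alert alone requires contact, not a change of medication.

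**Conclusion.** The point holds as a gap in the written rule: on its wording, the taper can start or continue after IMP has permanently stopped for a non-LoAC reason, with no restart prescribed before week 16 unless LoAC or CAE occurs. The possible controller-free time after the SAP window is 8 to 9 weeks for a last dose at weeks 0, 2 or 4, 8 at week 6, then 6, 4, 2 and 0. These are maxima: they assume the Table 1 schedules, no LoAC and no discretionary restart.

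Two stronger inferences are not supported. One is excess risk over the rest of the trial: placebo patients undergo the same taper without active drug, under the same monitoring, so the risk is no higher than theirs. The other is bias in the primary test: LoAC after the window does not enter it, and no such bias is claimed. What differs from placebo is the return, since the main efficacy analyses do not use this time.

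This is a cheap patient-safety improvement. Confidence is medium, because the pharmacy manual may already hold a rule.

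**What to change.** - Make every taper step conditional on no LoAC and continuing IMP.
- State in Protocol Sections 3.1, 4.4.2 and 3.6.1.2.9 and in Appendix J that when IMP is permanently stopped for any reason, further taper steps stop and controllers may be resumed, up to the run-in regimen, at the investigator's judgment.
- Add an IMP-status check to the taper evaluation and phone contacts.
- Limit the confirmation of discontinued controllers at Visits 7 to 9 to patients on IMP.
- Align the pharmacy manual.
- Leave the LoAC definition unchanged. Record the reason for any ICS resumption after an IMP stop. Extend the blinded data review that SAP 6.2.2 already plans for asthma-related adverse events, so that it decides whether a resumption within 14 days of the last dose counts under the 4x criterion.

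The cost is a wording amendment, one check in the CRF and phone script, one recorded reason and one added task for the blinded review. No visits or patients are added. The downsides are slightly lower LoAC detection in the 14 days after the last dose and variable resumed doses in post-discontinuation data.

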6.1.1. Loss of Asthma Control (Primary Efficacy Endpoint)

The primary efficacy endpoint is the proportion of patients who experience LoAC during the treatment period.

LoAC is defined as any one of the following during the treatment period:

- Morning PEF decrease $\geq 30\%$ from baseline on 2 consecutive days or morning handheld FEV₁ decrease $\geq 20\%$ from baseline on 2 consecutive days
- Increase in SABA/quick-relief medication ≥ 6 puffs over baseline use in 24 hours on 2 consecutive days*
- Increase in ICS dose $\geq 4x$ most recent dose*
- Systemic corticosteroid use
- Asthma ER visit or hospitalization

A patient who meets criteria for LoAC will discontinue IMP, and resume or increase background asthma controller therapies, but will remain in the study. LoAC events will be treated by the investigator according to local standard of care. An effort should be made to collect blood samples for TEV-48574 serum concentration and ADA testing at (or as close to) the time of LoAC as possible in addition to the scheduled assessments (see [Table 3](#) [treatment period] and [Table 4](#) [follow-up]).

In addition to the primary efficacy endpoint of the proportion of patients who experience LoAC, time to LoAC will be a key secondary endpoint (see Section 9.5.2).

*Once background asthma controller therapy has been standardized per protocol, the asthma controller regimen is to remain stable throughout the treatment period until the structured withdrawal per protocol or treatment of LoAC/CAE (Section 6.1.2). Patients who experience LoAC, including CAEs, during the treatment period will discontinue IMP and resume/increase background asthma controller therapy for the remainder of the study.

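### Protocol Section 3.1 says an alert never in itself means stopping study drug, but the FEV1/PEF alert has the same definition as LoAC criterion 1, for which Section 6.1.1 requires the stop

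*Protocol*

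**What the plan says.** Protocol Section 3.1 (Treatment Period) describes daily monitoring by hand-held spirometer and e-diary and lists three alerts:

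- Spirometry: a morning FEV1 fall of at least 20% "from baseline on 2 consecutive days OR decrease in morning PEF" of at least 30%, also on 2 consecutive days.
- Rescue use: "Increase in rescue medication use/SABA of 4 or more puffs over baseline for 2 or more consecutive days", or 12 or more puffs in any one day.
- Nighttime awakenings: 2 more than baseline on 2 consecutive days.

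It then says that an alert does not mean the patient's "medications need to be changed or that study drug should be discontinued, only that the patient should be contacted and evaluated". Whether that happens in a telephone call or an extra visit is left to the investigator. If the investigator suspects LoAC, the site should try to see the patient.

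Section 6.1.1 says "LoAC is defined as any one of the following during the treatment period". The first criterion is a morning PEF fall of at least 30%, or a morning hand-held FEV1 fall of at least 20%, on 2 consecutive days. The SABA criterion is an increase of at least 6 "puffs over baseline use in 24 hours on 2 consecutive days". The consequence is mandatory: "A patient who meets criteria for LoAC will discontinue IMP, and resume or increase background asthma controller therapies". Section 3.1 agrees in the paragraph after the alert text: "In the event of a LoAC or CAE, IMP will be discontinued and background asthma controller therapy will be restarted or increased".

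SAP Section 6.2.1 has site investigators determine and record LoAC.

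**The concern.** An alert sentence of this kind suits early warnings set below the endpoint threshold. The spirometry alert is not set below it. When that alert fires on acceptable treatment-period readings, the patient has met LoAC, yet the text beside the alert says that nothing more than contact and evaluation follows, and the linking sentence treats LoAC as something to be suspected.

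The same criterion is a safety stop during deliberate controller withdrawal and a component of the primary endpoint. The SAP describes no derivation of LoAC from the device data, so the site's record is the endpoint. With about 75 centres planned for 124 patients (124 / 75 = about 1.7 per centre), many teams would each apply this sentence to very few patients. What is at stake is consistent and prompt recognition of LoAC across sites.

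**Working it through.** No planned figure is in dispute, so the check sets the two sections side by side.

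| Alert (Section 3.1) | LoAC criterion (Section 6.1.1) | Does the alert by itself meet LoAC? |
|---|---|---|
| Morning FEV1 down ≥20%, 2 consecutive days, from baseline | Same, hand-held | Yes |
| Morning PEF down ≥30%, 2 consecutive days, from baseline | Same | Yes |
| SABA ≥4 puffs over baseline, 2 or more consecutive days | ≥6 puffs over baseline, 2 consecutive days | Only when the rise is ≥6 on both days |
| SABA ≥12 puffs in one day | None; LoAC needs 2 days | No |
| Nighttime awakenings | None | No |

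The contact-and-evaluate sentence is right for the last two rows and for a SABA rise from 4 to below 6 puffs. It is wrong for the first two rows and for a SABA rise of 6 or more on 2 consecutive days.

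Three conditions limit this:

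- The reading must fall in the treatment period, because LoAC is defined only there, while home recording runs from screening to end of study.
- The patient must have had no earlier LoAC. After one, the patient "will discontinue IMP and resume/increase background asthma controller therapy for the remainder of the study", so there is no study drug left to stop.
- The reading must be technically acceptable. Section 6.1.5 has hand-held values monitored for data quality, and inclusion criterion g requires repeatability for FEV1 but not PEF.

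**Possible delay.** The documents give no alert frequency, so the number of patients affected cannot be computed. The delay for one patient can be bounded.

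- Lower end: suppose a persistent fall triggers the alert on days 1–2. The next qualifying pair is days 2–3 (lag 3 − 2 = 1 day) or days 3–4 (lag 4 − 2 = 2 days). Whether alerts are re-sent on overlapping pairs is not stated, so both are assumptions.
- Upper end: an acceptable reading is judged not to be LoAC, no further alert or unscheduled visit intervenes, and LoAC is recognised at the next scheduled review. The Table 3 study days give a usual gap of 14 days (for example V2 to V3, 29 − 15). With ±3-day windows the longest gap is 14 + 3 + 3 = 20. From V1, which has no window, to V2 it is 14, or 14 + 3 = 17. From V4 to V5 and from V5 to V6 it is 7, or 7 + 3 + 3 = 13.
- In the Table 1 examples the patient is off all controllers from V5 (250/50 start) or V6 (500/50 start), so part of such a delay could be spent without a controller.
- If LoAC is recognised at that review, there are 0 extra doses and 0 extra taper steps. Sections 3.6.1.2.2 to 3.6.1.2.8 list the spirometry review ahead of the dose or taper step.

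**Weight of one event, for scale only.** At the planning rates, 62 × 0.27 + 62 × 0.108 = 16.7 + 6.7 = 23.4 events are expected, so one unrecorded event is 1 / 23.4 = about 4%. At the interim, assuming equal arms, 20 × 0.378 = 7.6 events (40 patients) or 26 × 0.378 = 9.8 (52 patients), so one event is about 13% or 10%. This does not estimate how often an event would go unrecorded.

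**The case against.** The strongest reply is that, read whole, the sentence says only that an automated alert is not by itself a stop order. The alerts are introduced as monitoring for potential LoAC, and checking a home reading before acting on it is sound practice. The next paragraph cites Section 6.1.1 and requires the stop, which recurs in Sections 3.3, 3.6.1.2.5 and 6.1.1 and in Table 3 footnote o. On that reading, a site that sees a qualifying reading and does not stop is breaching Section 6.1.1, not following Section 3.1. Spirometry review and LoAC inquiry also take place at every treatment-period contact, including the week 7 call.

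Much of this stands. A reader might infer that the protocol lacks a stop rule, or tells sites to continue dosing after LoAC. It does neither. A reader might also infer bias in favour of one arm. Sites are blinded, and nothing in the documents supports a direction.

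What does not stand is that the link is already made. None of the repeated stop rules says that the spirometry alert is itself LoAC. Data-quality checking justifies rejecting a bad reading; it does not make an acceptable reading that meets the criterion a matter of suspicion.

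**Conclusion.** The point holds as an inconsistency in wording, of minor to moderate severity. It rests on the definitions being identical, which can be read directly, and on the three conditions given in the working.

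The consequences are limited. The binary primary endpoint changes only if a qualifying event is never recorded in the treatment period. Delay alone could move the key secondary time to LoAC, but SAP Section 6.3.1 does not settle this: it measures to the occurrence of LoAC, and then places patients who discontinue treatment because of LoAC at the time of discontinuation. That is a separate dating question, which a change to the alert sentence does not resolve. The 14- to 20-day delay is a worst case that needs several things to go wrong together; with repeated alerts the lag is 1 to 2 days.

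**What to change.** In Section 3.1, add to the alert sentence: *unless LoAC criteria (Section 6.1.1) are met*. Then state that, during the treatment period and in a patient without prior LoAC, the following are LoAC and are handled under Section 6.1.1: technically acceptable morning hand-held readings, under the study's existing data-quality check, that meet the FEV1/PEF alert; and SABA use of 6 or more puffs over baseline on 2 consecutive days.

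Keep contact-and-evaluate for nighttime-awakening alerts and for SABA alerts below the LoAC threshold, including the single-day alert of 12 or more puffs. Do not make LoAC depend on a new site confirmation of validity. The endpoint definition has no such step, and an undefined one would bring back the site-to-site variation that the change is meant to remove.

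The cost is two pieces of wording and a notice to sites, with no new data, visits or patients and no change to any threshold or analysis. Investigators lose a little discretion over isolated acceptable readings. The sponsor would need to decide under Appendix D whether the change counts as administrative or needs ethics committee and authority approval as an amendment.
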